5.3 Lifestyle Considerations

5.3.1 Meals and Dietary Restrictions

5.3.1.1 Diet Restrictions

Dietary restrictions are not required.

5.3.1.2 Fruit Juice Restrictions

Fruit juice restrictions are not required.

5.3.2 Caffeine, Alcohol, and Tobacco Restrictions

5.3.2.1 Caffeine Restrictions

Participants will be instructed to avoid the ingestion of caffeine for at least 30 minutes before scheduled ECGs, HR, and BP procedures/assessments.

5.3.2.2 Alcohol Restrictions

08OVCJ

Participants will be counseled as needed to limit alcohol use to ≤ 1 standard drink per day or less than approximately 7 standard drinks per week in females, and ≤ 2 standard drinks per day or less than approximately 14 standard drinks per week in males, on average. One standard drink is defined as any beverage containing 14 g of pure alcohol or as defined by local guidelines.

5.3.2.3 Tobacco Restrictions

Participants will be instructed to avoid the ingestion of nicotine-containing products for at least 30 minutes before scheduled ECGs, HR, and BP procedures/assessments. For all time during the study, tobacco restriction is not required.

5.3.3 Activity Restrictions

Participants will avoid unaccustomed strenuous physical activity (ie, weightlifting, running, bicycling, etc) from the prestudy (screening) visit until administration of the initial dose of study intervention, throughout the study and until the poststudy visit.

5.4 Screen Failures

Screen failures are defined as participants who consent to participate in the clinical study but are not subsequently randomized in the study. A minimal set of screen-failure information may be included, as outlined in the eCRF entry guidelines. Minimal information may include demography, screen-failure details, eligibility criteria, and any AEs or SAEs meeting reporting requirements.

5.5 Participant Replacement Strategy

If a participant discontinues from study intervention or withdraws from the study, a replacement participant may be enrolled if deemed appropriate by the investigator and Sponsor. The replacement participant will generally receive the same intervention or intervention sequence (as appropriate) as the participant being replaced. The replacement participant will be assigned a unique treatment/randomization number.

6 STUDY INTERVENTION

Study intervention is defined as any investigational intervention(s), marketed product(s), placebo, or medical device(s) intended to be administered to a study participant according to the study protocol.

Clinical supplies (MK-6194 or placebo) will be packaged to support enrollment and replacement participants as required. When a replacement participant is required, the Sponsor or designee needs to be contacted before dosing the replacement participant. Clinical supplies will be affixed with a clinical label in accordance with regulatory requirements.

6.1 Study Intervention(s) Administered

The study intervention(s) to be used in this study are outlined in Table 2.

Country-specific differences are noted in Appendix 7.

All supplies indicated in Table 2 will be provided per the "Sourcing" column depending on local country operational requirements. If local sourcing, every attempt should be made to source these supplies from a single lot/batch number where possible (eg, not applicable in the case where multiple lots or batches may be required due to the length of the study, etc).

Refer to Section 8.1.8 for details regarding administration of the study intervention.

6.2 Preparation/Handling/Storage/Accountability

6.2.1 Dose Preparation

Specific calculations or evaluations required to be performed to administer the proper dose to each participant are outlined in a separate document provided by the Sponsor. The rationale for selection of doses to be used in this study is in Section 4.3.

MK-6194 sterile solution will be prepared and/or dosed per the instructions outlined in the Pharmacy Manual.

6.2.2 Handling, Storage, and Accountability

The investigator or designee must confirm appropriate temperature conditions have been maintained during transit for all study intervention received, and any discrepancies are reported and resolved before use of the study intervention.

Only participants enrolled in the study may receive study intervention, and only authorized site staff may supply or administer study intervention. All study interventions must be stored in a secure, environmentally controlled, and monitored (manual or automated) area in accordance with the labeled storage conditions with access limited to the investigator and authorized site staff.

The investigator, institution, or the head of the medical institution (where applicable) is responsible for study intervention accountability, reconciliation, and record maintenance (ie, receipt, reconciliation, and final disposition records).

For all study sites, the local country Sponsor personnel or designee will provide appropriate documentation that must be completed for drug accountability and return, or local discard and destruction if appropriate. Where local discard and destruction is appropriate, the investigator is responsible for ensuring that a local discard/destruction procedure is documented.

The study site is responsible for recording the lot number, manufacturer, and expiry date for any locally purchased product (if applicable) as per local guidelines unless otherwise instructed by the Sponsor.

[figure not shown]
The investigator shall take responsibility for and shall take all steps to maintain appropriate records and ensure appropriate supply, storage, handling, distribution, and usage of study interventions in accordance with the protocol and any applicable laws and regulations.

6.3 Measures to Minimize Bias: Randomization and Blinding

6.3.1 Intervention Assignment

Participants will be assigned randomly according to a computer-generated allocation schedule.

A sample allocation schedule is provided in Table 3.

q2w=once every 2 weeks

6.3.2 Stratification

No stratification based on age, sex, or other characteristics will be used in this study.

6.3.3 Blinding

A double-blinding technique will be used. MK-6194 and placebo will be prepared and/or dispensed in a blinded fashion by an unblinded pharmacist or qualified study-site personnel. The participant, the investigator, and Sponsor personnel or delegate(s) who are involved in the study intervention administration or clinical evaluation of the participants are unaware of the intervention assignments.

^a The suggested doses may be adjusted downward based on evaluation of safety, tolerability, PK, and/or pharmacodynamic data observed with previously administer doses.

^b Panels D, E and F may enroll up to 16 participants.

Study Intervention Compliance

PROTOCOL/AMENDMENT NO.: 008-04

6.4

[figure not shown]
Interruptions from the protocol-specified treatment plan require consultation between the investigator and the Sponsor and written documentation of the collaborative decision on participant management.

When the individual dose for a participant is prepared from a bulk supply, the preparation of the dose will be confirmed by a second member of the study-site staff.

When participants are dosed at the site, they will receive study intervention directly from the investigator or designee, under medical supervision. The date and time of each dose administered in the clinic will be recorded in the source documents and recorded in the CRF. The dose of study intervention and study participant identification will be confirmed at the time of dosing by a member of the study-site staff other than the person administering the study intervention.

6.5 **Concomitant Therapy**

[figure not shown]

Vaccine Guidelines:

- There are no available data on the concurrent use of MK-6194 and its impact on immune responses following vaccination. Therefore, in accordance with local vaccination standards, it is recommended that the participant's vaccination be brought up to date according to local vaccination standards.
- Primary or booster doses of the SARS-CoV2 vaccination may be administered throughout the study.
- Inactivated vaccines (such as inactivated influenza vaccines) should be administered according to local vaccination standards whenever medically appropriate.
- Live or attenuated vaccines (including, but not limited to varicella, MMR, MMRV, LAIV, yellow fever, Ty21a oral typhoid, BCG, smallpox, and rotavirus) are prohibited within 4 weeks of screening, throughout the study, and for 12 weeks after the last dose of study drug.

6.5.1 Rescue Medications and Supportive Care

Rescue Treatment for Atopic Dermatitis:

Supportive Care for Injection Reaction:

Refer to Section 8.3.2 (Injection Reactions).

CRUs will be staffed with medically trained personnel with appropriate access to full service acute-care hospitals to facilitate rapid institution of medical intervention.

6.6 Dose Modification (Escalation/Titration/Other)

All dose escalation decisions will be made jointly by the investigator and the Sponsor. Members of the Sponsor safety review team will include: the trial clinical director, trial clinical scientist, senior level clinical director and trial biostatistician. Additional Sponsor attendees may include the ESDS, ESDS lead, research associate and a pharmacologist. The Sponsor safety review team will obtain input from the investigator regarding investigators evaluation of safety and tolerability from the previous dosing period and investigators' recommendation to dose escalate in the next panel.

If, as judged by the Sponsor and investigator, the safety and tolerability data do not justify dose escalation, the dose will not be increased as planned. Instead, participants may:

- Receive the same dose level to further explore safety and tolerability at that level,
- Receive a lower dose of the study intervention (with or without food),
- Receive the same or lower dose as a divided dose, or
- Dosing may be stopped.

Participant discontinuation criteria are outlined in Section 7.

Enrollment and dosing of the expansion Panels D, E or F may be reduced or cancelled at the discretion of the Sponsor.

6.6.1 Stopping Rules

[figure not shown]
The following stopping rules will be used during the conduct of this study.

If any of the below stopping rules are met, the study will be paused, and no further dosing will occur until the Sponsor has reviewed the totality of data available. To continue the study (on joint agreement with the Sponsor and investigator), a substantial amendment will be submitted for approval.

08OVCJ

If any of the below stopping rules are met, subsequent higher doses will be lowered based on joint agreement of the Sponsor and investigator in order for the study to continue.

6.7 Intervention After the End of the Study

There is no study-specified intervention after the end of the study.

6.8 Clinical Supplies Disclosure

The emergency unblinding call center will use the intervention allocation/randomization schedule for the study to unblind participants and to unmask study intervention identity. The emergency unblinding call center should only be used in cases of emergency (see Section 8.1.10). The Sponsor will not provide random code/disclosure envelopes or lists with the clinical supplies.

This study is blinded, but supplies are provided open label; therefore, an unblinded pharmacist or qualified study-site personnel will be used to blind supplies. Study intervention identity (name, strength, or potency) is included in the label text; random code/disclosure envelopes or lists are not provided.

6.9 Standard Policies

Not applicable.

7 DISCONTINUATION OF STUDY INTERVENTION AND PARTICIPANT WITHDRAWAL

7.1 Discontinuation of Study Intervention

Discontinuation of study intervention does not represent withdrawal from the study. As certain data on clinical events beyond study intervention discontinuation may be important to the study, they must be collected through the participant's last scheduled follow-up, even if the participant has discontinued study intervention. Therefore, all participants who discontinue study intervention before completion of the protocol-specified treatment period will still continue to participate in the study as specified in Section 1.3 and Section 8.1.9, or if available, a PCL.

Participants may discontinue study intervention at any time for any reason or be discontinued from the study intervention at the discretion of the investigator should any untoward effect occur. In addition, a participant may be discontinued from study intervention by the investigator or the Sponsor if study intervention is inappropriate, the study plan is violated, or for administrative and/or other safety reasons. Specific details regarding procedures to be performed at study intervention discontinuation are provided in Section 8.1.9.

A participant must be discontinued from study intervention, but continue to be monitored in the study, for any of the following reasons:

- The participant or participant's legally acceptable representative requests to discontinue study intervention.
- Participants who receive a systemic rescue treatment or phototherapy
 - Note: Participants who use topical corticosteroids prior to Week 6 will be permitted to continue in the study.
- The participant's treatment assignment has been unblinded by the investigator, MSD subsidiary, or through the emergency unblinding call center.
- The participant missed four doses of study intervention within the first eight weeks of the study.
- The participant has a Grade 3 or higher AE (Grade 2 or higher for the system-organ class of Cardiac Disorders) considered related to study intervention.
- The participant has a medical condition or personal circumstance which, in the opinion of the investigator and/or Sponsor, placed the participant at unnecessary risk from continued administration of study intervention.
- The participant has a positive UDS, except for cannabis, at any time during the course of the study. The drug screen can be confirmed by a recheck at the discretion of the investigator after discussion with the Sponsor.

Note: participants may be allowed to continue the study intervention with a positive UDS due to the use of specific medications (see Section 6.5) if they have an active prescription from a licensed health care provider and the Investigator and Sponsor both agree that the participant may continue to participate in the study.

The participant meets at least one study specific stopping criterion as listed in Section 6.6.1

Discontinuation from study intervention is "permanent." Once a participant is discontinued from study intervention, they shall not be allowed to restart study intervention.

7.2 **Participant Withdrawal From the Study**

Participants may withdraw from the study at any time for any reason. If a participant withdraws from the study, they will no longer receive study intervention or be followed at scheduled protocol visits.

A participant must be withdrawn from the study if:

The participant or participant's legally acceptable representative withdraws consent from the study.

Specific details regarding procedures to be performed at the time of withdrawal from the study, as well as specific details regarding withdrawal from FBR, are outlined in Section 8.1.9. The procedures to be performed should a participant repeatedly fail to return for scheduled visits and/or if the study site is unable to contact the participant are outlined in Section 7.3.

7.3 **Lost to Follow-up**

If a participant fails to return to the clinic for a required study visit and/or if the site is unable to contact the participant, the following procedures are to be performed:

- The site must attempt to contact the participant and reschedule the missed visit. If the participant is contacted, the participant should be counseled on the importance of maintaining the protocol-specified visit schedule.
- The investigator or designee must make every effort to regain contact with the participant at each missed visit (eg, telephone calls and/or a certified letter to the participant's last known mailing address or locally equivalent methods). These contact attempts should be documented in the participant's medical record.
- Note: A participant is not considered lost to follow-up until the last scheduled visit for the individual participant. The missing data for the participant will be managed via the prespecified statistical data handling and analysis guidelines.

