1.3 Schedule of Activities

Study Period:	Screening							Iı	nterv	venti	ion						Post- study	Notes
Scheduled Day		1	8	15	22	29	36	43	57	71	85	92	99	113	127	141	169	
Administrative Procedures	•														ı	ı		,
Informed Consent	X																	Sec. 5.1, 8.1.1.1
Informed Consent for FBR	X																	Sec. 5.1, 8.1.1.2
Participant ID Card	X																	Sec. 8.1.3
Inclusion/Exclusion Criteria	X	X																Sec. 5.1, 5.2, 8.1.2 Review of IC/EC at Screening, only specific criteria will be reviewed at predose prior to randomization
Medical History	X																	Sec 8.1.4
Prior/Concomitant Medication Review	X																X	Sec 5.2, 6.5, and 8.1.5
Assignment of Screening Number	X																	Sec 8.1.6
Assignment of Treatment/ Randomization Number		X																Sec 5.5, 8.1.7
CCI																		
Safety Procedures																		
Full physical examination	X	X															X	Sec. 8.3.1 Day 1 at predose
Height	X																	Sec. 8.3.1
Weight	X																X	Sec. 8.3.1
VS (HR, BP)	X	X	X	X	X	X	X	X	X	X	X	X	X	X	X	X	X	Sec. 8.3.3.1 Days 1, 15, 29, 43, 57, 71 and 85: within 3h predose and 0.5 h postdose
VS (RR and Body Temperature)	X	X	X	X	X	X	X	X	X	X	X	X	X	X	X	X	X	Sec. 8.3.3.1 Days 1, 15, 29, 43, 57, 71 and 85: within 3h predose and 0.5 h postdose
12-lead ECG	X	X	X	X	X	X	X	X	X	X	X	X	X	X	Х	X	X	Sec. 8.3.4, Appendix 9 Day 1: Predose and 12 hr postdose All other days: one ECG measurement Triplicate at Day 1 predose and Day 1 12 h postdose, single measurement at all other timepoints
Local injection site reaction assessment		X	X	X	X	X	X	X	X	X	X	X	X	X	X	X	X	Sec. 8.3.2 Days 1, 15, 29, 43, 57, 71 and 85: predose and 0.5 h postdose

PROTOCOL/AMENDMENT NO.: 008-04

Study Period:	Screening							Iı	nterv	venti	on						Post- study	Notes
Scheduled Day		1	8	15	22	29	36	43	57	71	85	92	99	113	127	141	169	
AE/SAE review including assessment for systemic injection reaction	X																X	Sec 8.4, 10.3
Laboratory Procedures																	1	T
Serum FSH - (WONCBP only)	X																	Sec. Appendix 2, Appendix 5
Serum or urine β-hCG pregnancy test (WOCBP only)	X	X		X		X		X	X	X	X			X		X	X	Sec 8.3.6, Appendix 2 Day 1 predose serum pregnancy test may be obtained within 72 hours of dosing.
HIV, hepatitis B and C screen (per site SOP)	X																	Sec. 8.3.5, Appendix 2

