4 STUDY DESIGN

4.1 Overall Design

Specific procedures to be performed during the study, including prescribed times and associated visit windows, are outlined in Section 1.3 of the SoA. Details of each procedure are provided in Section 8.

4.1.1 **Decisions Regarding Dose Escalation**

Dose Escalation from Panel A to Panel B: The participants in Panel A will be dosed with MK-6194 2.5 mg/ placebo once every 2 weeks. Dose escalation decisions to Panel B will be made after review of safety data, including adverse events, physical examination, vital signs, injection site reactions, laboratory tests and ECGs from participants through at least one week following the final dose of MK-6194/ placebo Review of data will be further supplemented with safety data from Dose Escalation from Panel B to Panel C:

Dose escalation based on the safety data review outlined above is supported by:

4.1.2 **Decision Regarding Dosing of Expansion Panels**

The safety data required for dosing of expansion panels at the same dose will be less than that required for dose escalation.

MK-6194-008-04 FINAL PROTOCOL 12-DEC-2022

32

12-DEC-2022

Expansion panels D, E, and F may initiate dosing following review of safety data from 4 participants from a primary escalation panel at an equal or greater dose that have been monitored for 7 days following the first dose (Day 8).

Expansion panels D, E and F may enroll up to 16 participants in each panel. Expansion panels will be administered doses that are the same (or lower) than the dose in the corresponding escalation panel.

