8.10.6 Study Design/Dosing/Procedures Modifications Permitted Within Protocol Parameters

This is a Phase 1 assessment of MK-6194 in humans, and the PK, pharmacodynamic, and safety profiles of the compound are still being elucidated. This protocol is written with some flexibility to accommodate the inherent dynamic nature of Phase 1 clinical studies.

MK-6194-008-04 FINAL PROTOCOL 12-DEC-2022

Modifications to the dose, dosing regimen, and/or clinical or laboratory procedures currently outlined may be required to achieve the scientific goals of the study objectives and/or to ensure appropriate safety monitoring of the study participants.

As such, some alterations from the currently outlined dose and/or dosing regimen may be permitted based on newly available data, but the maximum total biweekly dose may not exceed those currently outlined in the protocol.

- Repeat of or decrease in the dose of the study intervention administered in any given period/panel
- Interchange of doses between panels
- Entire panel(s) may be omitted
- Decrease in the duration of study intervention administration (eg, number of doses)
- Adjustment of the dosing interval (eg, q3w, but not to be more frequent than q2w)
- Remove a planned PK pause if agreed by Sponsor and investigator if no further increases in total daily dose
- Addition of study pause
- Modification of the PK/pharmacodynamic sample processing and shipping details based on newly available data

The PK/pharmacodynamic sampling scheme currently outlined in the protocol may be modified during the study based on newly available PK or pharmacodynamic data (eg, to obtain data closer to the time of peak plasma concentrations). If indicated, these collected samples may also be assayed in an exploratory manner for metabolites and/or additional pharmacodynamic markers.

Up to additional 50 mL of blood may be drawn for safety, PK, and/or pharmacodynamic analyses. The total blood volume withdrawn from any single participant will not exceed the maximum allowable volume during his/her participation in the entire study (Appendix 8).

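### Is the mandatory rule on four missed doses in the first eight weeks unworkable against the two-weekly dosing schedule?

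*Combined protocol and SAP*

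**What the plan says.** Section 7.1 introduces its list with "A participant must be discontinued from study intervention, but continue to be monitored in the study, for any of the following reasons". One item is "The participant missed four doses of study intervention within the first eight weeks of the study". The same section makes the step irreversible: "Once a participant is discontinued from study intervention, they shall not be allowed to restart study intervention".

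The dosing days come from the notes in the Schedule of Activities (Section 1.3), for example the vital signs row: "Days 1, 15, 29, 43, 57, 71 and 85: within 3h predose and 0.5 h postdose". Section 8.10.6 lists changes that may be made without redesigning the study, among them "Adjustment of the dosing interval (eg, q3w, but not to be more frequent than q2w".

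Three other places bear on the point:

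- Section 4.1.2, on starting the expansion panels, refers to participants "monitored for 7 days following the first dose (Day 8", which shows how the protocol turns elapsed time into study days.
- Section 6.4 covers departures from the dosing plan: "Interruptions from the protocol-specified treatment plan require consultation between the investigator and the Sponsor". The joint decision must be documented in writing.
- Section 5.5 says that when a participant stops dosing or withdraws, "a replacement participant may be enrolled if deemed appropriate by the investigator and Sponsor".

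**The concern.** A rule that forces permanent discontinuation should be one that a site can apply and that a participant can meet. Here the number of misses (four) is close to the number of doses the window can hold, and the visible text does not give the window's last day. The Day 57 dose sits exactly on the boundary. If it is excluded, the rule cannot be met by anyone who received the first dose. If it is included, every later dose up to and including Day 57 must be missed. At a three-weekly interval the rule cannot be met on either count.

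Two things would be at stake. Two sites could treat the same participant differently, one stopping dosing for good and the other dosing on Days 71 and 85. And because discontinuation is one route to replacement, the reading could affect who is replaced.

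**Working it through.** **Inputs.** Dosing days 1, 15, 29, 43, 57, 71 and 85 (Section 1.3); planned interval of two weeks (Section 4.1.1, Panel A); permitted example of three weeks (Section 8.10.6); threshold of four misses in eight weeks (Section 7.1); poststudy visit about 84 days after the last dose (Section 8.10.4), scheduled on Day 169 (Section 1.3).

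**Reproducing the schedule.** Day = 1 + 14k for k = 0 to 6 gives 1, 15, 29, 43, 57, 71, 85, the seven stated days. The last dose plus 84 days is 85 + 84 = 169, the stated poststudy day.

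**Counting doses in the window.** Three-weekly days are 1 + 21k: 1, 22, 43, then 64. For a participant who received Day 1, n later doses in the window give 2^n patterns of taken and missed doses.

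| Interval and window | Doses in window | Later doses, n | Patterns, 2^n | Patterns with four misses |
|---|---|---|---|---|
| Two-weekly, Days 1–56 | 1, 15, 29, 43 | 3 | 8 | 0 |
| Two-weekly, Days 1–57 | 1, 15, 29, 43, 57 | 4 | 16 | 1 |
| Three-weekly, to Day 56 or 57 | 1, 22, 43 | 2 | 4 | 0 |

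On the second row the single qualifying pattern is Days 15, 29, 43 and 57 all missed. The rule can first apply on Day 57, with 7 − 5 = 2 planned doses left.

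**Which window the protocol implies.** Section 4.1.2 equates seven days after the first dose with Day 8, that is 1 + 7. The poststudy visit follows the same elapsed-day count. Applied to eight weeks, it gives 1 + 56 = Day 57, which is a scheduled visit; Day 56 is not. Section 9.7 also refers to an interim look at week 8, and the nearest scheduled visits are Days 43, 57 and 71.

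**How often it could matter.** The documents give no miss rate. Assume, for illustration only, that each dose is missed independently with probability p. The chance of missing all four later doses through Day 57 is p^4:

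- p = 0.05: 0.00000625, or 72 × 0.00000625 = 0.00045 of the maximum 72 participants
- p = 0.10: 0.0001, or 0.0072 participants
- p = 0.20: 0.0016, or 0.12 participants
- p = 0.30: 0.0081, or 0.58 participants

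Misses are unlikely to be independent. Someone who stops attending misses every later dose, which is the one qualifying pattern. So neither 1 in 16 nor p^4 estimates how often the rule would be used.

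**The case for a change.** The strongest case for a change is that the rule has permanent consequences and its end day takes one sentence to state. A participant can miss Days 15, 29 and 43 in a row without meeting it on either reading. A move to three-weekly dosing needs only a letter to the study file, and nothing visible in Section 8.10.6 would prompt anyone to revisit Section 7.1.

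Part of this stands. No visible sentence says whether Day 57 counts, and the rule would have no function at a three-weekly interval. The rest carries less weight:

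- A lenient threshold is the sponsor's choice and is not a conflict between passages. On the Day 57 count the rule still has a use. Section 7.3 does not class a participant as lost to follow-up until the last scheduled visit, and this rule formally ends dosing for someone who received Day 1 and nothing since.
- Sites do not decide alone. Under Section 6.4 a participant nearing four misses would already be under joint, documented review.
- Section 7.1 separately lets the investigator or sponsor stop dosing for breach of the study plan or for administrative reasons, so a participant outside the mandatory rule can still be discontinued.
- Replacement under Section 5.5 is discretionary and open after any discontinuation, so this rule is not the only way to it.
- Three-weekly dosing is only an example of a permitted change. The letter that would introduce it also goes to the investigator and could deal with linked rules.

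**Conclusion.** The arithmetic is correct, but it does not show a fault that needs correcting. On the protocol's own day count the eight weeks end on Day 57, and there the rule can be met and agrees with the schedule. What remains is an unstated end day that investigator and sponsor can settle in the consultation they must hold anyway.

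The size is small. At the planned interval, the readings differ for a participant dosed on Day 1 only if every dose from Day 15 through Day 57 is missed, and then at most two of seven doses depend on the answer. Discontinued participants stay under observation, data are analysed by treatment received (Section 9.5), and stopping for missed visits alone is not a discontinuation due to an adverse event. No planned summary or conclusion becomes wrong.

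This rests on three assumptions: the window starts at Day 1; the elapsed-day count used elsewhere applies here; and two-weekly dosing is kept. Parts of Sections 4.1 and 6.4, and the dosing and collection-window tables, are not visible and may define a missed dose or map weeks to days. No view is taken on the threshold itself.
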